5.1 Overall Trial Design and Plan

This will be a randomized, double-blind, placebo-controlled study in participants with RMS, with a parallel, open-label active control group (Tecfidera) involving 5 treatment groups with 3 doses of M2951, placebo, and active control (Tecfidera). The assessing Investigator and central MRI reader will be treatment blinded.

The study will consist of 4 major periods: (i) a Screening period of 4 weeks, (ii) active treatment with 3 dose groups of M2951, active control (Tecfidera), or placebo for 24 weeks, (iii) a 24-week extension on active treatment with M2951 or active control (Tecfidera) for 24 weeks, where participants on placebo will be switched to M2951 (Figure 1), and (iv) an optional OLE Period of a duration up to 384 weeks. At the end of the 48-week main study, participants will be in 1 of 4 treatment groups (M2951 25 mg daily, 75 mg once daily, or 75 mg twice daily or Tecfidera). Participants who entered the OLE Period initially received M2951 at 75 mg once daily. After review of the efficacy and safety data from the primary analysis at 24 weeks and the blinded extension analysis at 48 weeks, the optimal tested dose is 75 mg twice daily. Accordingly, once IMP for this dose is available at the study site, participants in the OLE Period will either enter the OLE Period on the 75 mg twice daily dose or will be switched to the 75 mg twice daily dose (Figure 2). Participants transitioning from Tecfidera will complete a washout period of at least 4 weeks prior to initiating M2951 treatment in the OLE Period (see Section 5.5.1 and (Figure 2). Following completion or early termination of treatment, participants will return after 4 weeks for safety evaluation. It is planned that placebo participants will be switched to the 25 mg M2951 once daily dose after Week 24.

Approximately 50 participants will be enrolled in each treatment group to obtain 44 evaluable participants per group (total = approximately 250), assuming a 12% drop-out rate per year, and to compile an adequate safety database. Approximately 200 participants are expected to be enrolled in the OLE.

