If a participant experiences more than one occurrence of the same TEAE during the trial for a given trial period of interest, the participant will only be counted once for that treatment (the worst severity and the worst relationship to trial treatment will be tabulated).

In case a participant had events with missing and non-missing grades, the maximum of the non-missing grades will be displayed. AEs with missing classification concerning study intervention relationship will be considered related to the study intervention.

Incomplete AE-related dates will be handled as described in Section 11.9.

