17.1.1.2 EAIR of TEAEs

EAIR of TEAEs are calculated as the number of participants with TEAE divided by the sum of the individual times of all participants in the treatment group from start of treatment to first onset of TEAE in the corresponding time period. The incidence rate multiplied with 100 would give the number of AEs expected in 100 participants within 1 time unit (year). EAIR of TEAEs will be presented by SOC and PT. Confidence interval of incidence rate will be calculated using the GENMOD procedure from SAS ® with Ismeans instruction using a Poisson binomial model. If a participant has multiple events, the exposure period of the first event will be used. For a participant with no event, the exposure period will be censored at the last follow-up time within the AE summarization period.

The EAIR of TEAE tables to be prepared are listed in Table 3 below:

Table 3: EAIR of TEAE Tables to be Produced

	Overall frequency	By primary SOC and PT	By primary SOC, PT and worse grade	OLE Period	OLE Period by year
TEAEs	Χ	Χ	X	X	Χ
IMP-related TEAEs	X	Χ	NA	X	NA
Serious TEAEs	X	Χ	NA	X	NA
IMP-related Serious TEAEs	Χ	Χ	NA	Χ	NA
TEAEs of Special Interest	×	NA (by AESI category, CMQ/SMQ and PT)	NA	X	NA

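### Time at risk for the worst-grade EAIR rows is not grade-specific: read literally, higher-grade rates in that one table can only err upward, by an amount the documents do not settle

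*SAP*

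**What the plan says.** SAP Section 17.1.1.2 defines the EAIR as "number of participants with TEAE divided by the sum of the individual times of all participants in the treatment group", with each individual time running "from start of treatment to first onset of TEAE in the corresponding time period". Two rules complete the definition. For repeat events: "If a participant has multiple events, the exposure period of the first event will be used". For participants without one: "For a participant with no event, the exposure period will be censored at the last follow-up time within the AE summarization period". The section then describes the rate times 100 as an expected number of AEs.

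Table 3 in the same section has a column headed "By primary SOC, PT and worse grade". It is marked for the TEAEs line only; the IMP-related, serious, IMP-related serious and AESI lines show NA.

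The grade row is set in Section 17.1. When a participant has more than one occurrence of the same TEAE in the period of interest, the participant is counted once and "the worst severity and the worst relationship to trial treatment will be tabulated".

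Neither section gives a time-at-risk rule for grade rows.

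**The concern.** The numerator and the denominator of a higher-grade row follow different events. Worst grade is known only once the whole period has been observed, whereas the clock stops at the first event. Take a participant with a Grade 1 event at Week 2 and a Grade 3 event of the same PT at Week 200. Read literally, that participant adds one case to the Grade 3 row and 2 weeks of exposure, although Grade 3 was first reached after 200 weeks.

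A second gap concerns participants who only ever have milder events. The text does not say whether they count as having no event in the Grade 3 row, and so contribute full follow-up, or whether their time also stops at the mild event.

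The extension is long (the protocol plans "an optional OLE Period of a duration up to 384 weeks"), so the interval between a first mild event and a later severe one can be large. Two programmers could produce different higher-grade rates from the same text. Under the literal reading, the rates would not be comparable with rates computed elsewhere on a grade-specific clock.

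**Working it through.** The SAP states no EAIR, TEAE rate or grade mix, so there is no plan figure to reproduce. The check compares one numerator, participants with a Grade 3 or higher event, over different clocks.

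**Inputs**
- From the protocol, Section 5.1: OLE of up to 384 weeks = 2688 days, and 2688/365.25 = 7.36 years.
- From the SAP, Appendix 3: last OLE analysis visit at Week 336, nominal day 2352, and 2352/365.25 = 6.44 years. SAP Section 5 notes early termination; actual mean follow-up is not given.
- Assumed: constant any-grade rate L in the row, Grade 3 or higher share f (5% unless stated), and follow-up T of 4 to 7.36 years.

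**Three clocks**
- A: everyone stops at the first event of any grade in the row.
- B: everyone stops at the first Grade 3 or higher event in the row.
- C: Grade 3 or higher cases stop at their first event of any grade; milder-only participants keep full follow-up.

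The numerator is common, so the overstatement is a ratio of person-time. Clocks A and C can never run longer than B, so that ratio cannot fall below 1.

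**Closed form, A against B**

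`ratio = [(1 − exp(−fLT)) / (fL)] / [(1 − exp(−LT)) / L]`

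- L = 0.05, T = 5: (0.01242/0.0025) / (0.22120/0.05) = 4.969/4.424 = 1.12
- L = 0.1, T = 4: (0.01980/0.005) / (0.32968/0.1) = 3.960/3.297 = 1.20
- L = 0.5, T = 5: (0.11750/0.025) / (0.91792/0.5) = 4.700/1.836 = 2.56
- L = 1, T = 7.36: (0.30788/0.05) / (0.99936/1) = 6.158/0.999 = 6.16

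| Row type (assumed any-grade rate) | Ratio A/B, T = 4 to 7.36 years |
|---|---|
| PT-like, 0.5 to 5 per 100 PY | 1.01 to 1.18 |
| SOC-like, 10 to 50 per 100 PY | about 1.2 to 3.4 |
| Any TEAE, 100 per 100 PY (f = 5% to 20%) | about 2.8 to 6.2 |

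For a table by year of OLE (48 weeks), the same formula gives 1.00 to 2.1 over rates up to 200 per 100 PY.

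**Simulation** (200,000 participants, T = 6 years, 8% per year dropout, with and without gamma frailty of variance 1)
- A against B at 100 per 100 PY, f = 5%: 4.51 without frailty and 2.53 with it.
- C against B in the same setting: 1.10 and 1.09.
- C against B over all settings tried: 1.00 to 1.25.

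The size therefore depends mostly on how milder-only participants are handled and on how common the event is in the row.

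**The case against.** The strongest reply is that the clock is underspecified rather than wrong. The onset wording carries no SOC or PT qualifier either, yet SOC and PT rows plainly need the onset of that SOC or PT. If the same row-specific sense is extended to grade, the clock stops at the first event belonging to the row and the bias disappears. That reading is possible and stands as such. It is the less natural one: the section says the rates are presented by SOC and PT without mentioning grade, the repeat-event sentence points to the first event exactly where first and worst diverge, and Section 17.3 writes a grade threshold into its ALT time-to-event definitions when one is meant.

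The remaining replies limit the size and reach, and they stand:
- A reader might infer a general several-fold overstatement. The documents give no TEAE rate, grade mix or mean follow-up, so no general factor can be derived. Even a ratio of 1.2 at 4 years needs about 33% of the group to have that event at some grade (1 − exp(−0.4) = 0.33), well above the PT-like rates used here.
- A reader might take the largest ratios as applying to the planned table. They need an any-TEAE row split by grade. Table 3 lists overall frequency and the SOC, PT and grade split as separate columns, so such a row is not clearly specified. Section 17.1 ties the worst-severity rule to repeats of the same TEAE, not to different TEAEs.
- A reader might infer that milder-only participants stop contributing time. The SAP does not say so.
- A reader might think this is the SAP's only exposure-adjusted view of severity. It is not: Table 3 also plans AESI EAIRs, Section 17.2.3 includes serious or Grade 3 and higher infections among the AESIs, and the immunoglobulin section carries a further EAIR of infections.
- No hypothesis test uses these rates, and any error overstates harm rather than hiding it.

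**Conclusion.** The point holds in a limited form. On the most natural literal reading, the worst-grade EAIR pairs a worst-grade count with time to the first event of any grade in that SOC or PT, and the resulting bias in higher-grade rates can only be upward. A row-specific clock would remove it, but the SAP does not state one.

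The size rests wholly on assumed constant rates, a 5% Grade 3 or higher share and 4 to 7.36 years of follow-up. If milder-only participants also stop at their first event, it is about 1.0 to 1.2 times for PT-like rows and about 1.2 to 3.4 times for SOC-like rows, and larger only for an any-TEAE by-grade row if one is produced. If milder-only participants keep full follow-up, it is about 1.0 to 1.25 times.

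The issue is confined to the TEAEs worst-grade cell of Table 3. Worst-grade counts and percentages in Table 2 are unaffected. Separately, describing the rate times 100 as an expected number of AEs does not match a numerator that counts participants.

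**What to change.** In SAP Section 17.1.1.2, add for the by-grade EAIR:
- Numerator: participants with at least one TEAE of that grade or higher in that SOC or PT. Presenting the rows as Grade ≥ k is one clean way to do this.
- Time at risk: from start of treatment to the first onset of such an event.
- Participants without such an event, including those with only milder events, are censored at the end of the summarization period.

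Keep the first-event rule for EAIR tables not split by grade. Describe the rate times 100 as participants with a first event per 100 participant-years.

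Cost: SAP wording and minor programming, with no new data. Reported higher-grade rates may come out lower than under the literal rule.

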17.1.1.3 Adverse Events Leading to Treatment Discontinuation or Other Action Taken

Summary tables will be provided as detailed in Section 17.1.1.1.

A listing of TEAEs leading to withdrawal of IMP and a listing of TEAEs leading to study termination during the OLE period, will be provided.

17.2 Deaths, Other Serious Adverse Events, and Other Significant Adverse Events

17.2.1 **Deaths**

A summary of deaths occurring during OLE period will be provided including (clinicaltrials.gov requirement):

- Number and percentage of (all) deaths
- Number and percentage of the primary cause of death (categories: progressive disease and/or disease related condition, event unrelated to IMP, event related to IMP, unknown)

TEAEs leading to death and IMP-related TEAEs leading to death will be tabulated by SOC and PT along with overall frequency as described in Section 17.1.1.1. A listing of deaths occurring during the DBP and OLE period, if any, will be provided. In case there is no death in the trial, only the summary of death required by clinicaltrials gov will be performed, neither tabulation of TEAE leading to death will be edited, nor the listing of death.

17.2.2 Serious Adverse Events

The tabulation of serious TEAEs is described in Section 17.1.1.1. A participant listing of serious TEAEs during the OLE period will be provided.

17.2.3 TEAEs of Special Interest

The following events are defined as AEs of Special Interest (AESI):

- Liver related AEs
- Infections:
 - All Infections reported as Serious AEs or Grade ≥ 3
 - All opportunistic infections
- Amylase and lipase elevations including acute pancreatitis
- Seizures

AESI will be identified using Standardized MedDRA query (SMQ) if available or sponsor-defined list of search term (refer to Appendix 19.5). AESI terms will be summarized under all categories they fall under.

An overview of AESI will be presented by treatment group showing number and percentage of participants experiencing AESI for the OLE period. Study intervention related AESI will also be presented. AESIs will be flagged in the AE listings.

Additional analysis on the infections will be performed.

The following output will be provided:

Kaplan-Meier figure for time to onset of infections. An event is defined as first occurrence of any PT in the SMQ "Severe Infections" or AESI "Opportunistic infections" from first day of exposure with Evobrutinib (i.e. for patients in the Placebo and Tecfidera groups the time period starts after switch to Evobrutinib 25 mg QD (week 25) and switch to Evobrutinib 75 mg QD, respectively. For all other patients the time period starts at study start (with first intake of Evobrutinib)). An overall Kaplan-Meier curve will be displayed.

17.3 Clinical Laboratory Evaluation

The clinical laboratory safety parameters measured in this trial and reported as part of the safety evaluation of hematology, biochemistry, and urinalysis, are specified in the protocol (Table 8 of the Clinical Trial Protocol, Section 7.4.3). The entire clinical laboratory section will be analyzed for OLE period. Some outputs not produced at time or Primary analysis and Blinded Extension analysis will also be repeated on the DBP for participants of the SAF analysis set.

Summaries of Clinical Laboratory Data

Laboratory values (including corresponding normal ranges) converted in standard units will be used for summary statistics, shift tables and boxplots. Gradable laboratory results will be classified according to the grades defined in NCI-CTCAE Version 4.03 as provided by the central laboratory. If a laboratory parameter has bi-directional toxicities (e.g., Potassium), both directions will be presented for the given parameter (i.e., Potassium Low and Potassium High). On-treatment values are defined as results of assessments made after the first IMP administration on Day 1. Laboratory results containing a modifier such as "<" or "\ge " will be handled case by case for summary statistics and will be reported both as collected in the database and as imputed in participant data listings. Data until the Safety Follow-up included will be used to derive the worst on-treatment values.

All parameters will also be presented according to the categories based on normal ranges: below normal limits (Low), within normal limits (Normal) and above normal limits (High).

Shift tables of baseline value (low, normal, high) versus worst on-treatment value, presented by treatment group, will be provided for hematology and biochemistry parameters.

Shift tables of baseline grade versus worst post-baseline grade, presented by treatment group, will be provided for hematology and biochemistry parameters.

Shift tables will be displayed using the OLE Baseline and worst on-treatment value or worst post-baseline grade during OLE period.

Directional laboratory tests (hematology, biochemistry) (Appendix 19.1) will be summarized by worst on-treatment value and by treatment group.

Protocol-specified clinical laboratory hematology, biochemistry and urinalysis parameters will be summarized using descriptive statistics appropriate to continuous-valued random variables (see Section 11.5) by time point and by treatment group during the OLE period. At each time point, both observed value and CFB value will be summarized.

Graphical Display of Clinical Laboratory Data

Boxplots of laboratory values by treatment group and timepoint will be provided for the hematology and biochemistry parameters displayed in Table 4.

Table 4: Parameters for boxplots

Category	Laboratory parameter	Conventional Unit	SI Units
	Hemoglobin	g/dL	g/L
	Red blood cell count	$10^6/\mu L$	$10^{12}/L$
	Reticulocyte count	$10^3/\mu L$	10 ⁹ /L
Hematology	White blood cell count	$10^3/\mu L$	10 ⁹ /L
Tenmorogy	Neutrophil count	$10^3/\mu L$	10 ⁹ /L
	Lymphocyte count	$10^3/\mu L$	10 ⁹ /L
	Eosinophils	10 ⁹ /L	10 ⁹ /L
	Basophils	10º/L	10 ⁹ /L
	Platelet count	$10^3/\mu L$	10 ⁹ /L
	Alanine aminotransferase (ALT)	U/L	U/L
	Albumin	g/dL	g/L
	Aspartate aminotransferase (AST)	U/L	U/L
	Gamma- glutamyl transferase (GGT)	U/L	U/L
Biochemistry	Alkaline phosphatase	U/L	U/L
	Total bilirubin	mg/dL	μmol/L
	Amylase	U/L	U/L
	Lipase	U/L	U/L
	eGFR	mL/min	mL/min
	Blood urea nitrogen (BUN)	mg/dL	mmol/L
	Creatinine	mg/dL	μmol/L
	Glucose	mg/dL	μmol/L
	Sodium	mEq/L	mmol/L
	Potassium	mEq/L	mmol/L

Boxplots will be displayed from the OLE Baseline up to OLE Week 48 and from OLE Week 52 to OLE Week 96 etc. to remain readable.

The ULN and LLN will be added to the lab parameter boxplot, for any lab parameter where the normal range is the same for all participants in the analysis set. All graphical displays will be shown on a log-scale when needed to make the plot readable. All plots of a given parameter will have the same scale to allow comparison between groups and periods.

Liver function tests

AST, ALT and total bilirubin are used to assess possible drug induced liver toxicity. The ratios of test result over upper limit of normal (ULN) will be calculated and classified for these 3 parameters during the OLE period.

Summary of liver function tests will include the following categories. The number and percentage of participants with each of the following categories during the OLE period will be summarized by treatment group:

- AST $\geq 3 \times ULN$, AST $\geq 5 \times ULN$, AST $\geq 10 \times ULN$, AST $\geq 20 \times ULN$
- ALT \geq 3×ULN, ALT \geq 5×ULN, ALT \geq 10×ULN, ALT \geq 20×ULN
- (ALT or AST) ≥ 3×ULN, (ALT or AST) ≥ 5×ULN, (ALT or AST) ≥ 10×ULN, (ALT or AST) ≥ 20×ULN
- TBILI ≥ 2×ULN
- Concurrent AST ≥ 3×ULN and TBILI ≥ 2×ULN
- Concurrent ALT \geq 3×ULN and TBILI \geq 2×ULN
- Concurrent (ALT or AST) $\geq 3 \times ULN$ and TBILI $\geq 2 \times ULN$
- Concurrent (ALT or AST) $\geq 3 \times ULN$ and TBILI $\geq 2 \times ULN$ and ALP $\geq 2 \times ULN$
- Concurrent (ALT or AST) $\geq 3 \times ULN$ and TBILI $\geq 2 \times ULN$ and ALP $\leq 2 \times ULN$ or missing

Concurrent measurements are those occurring on the same date.

Categories will be cumulative, i.e., a participant with an elevation of AST \geq 10×ULN will also appear in the categories \geq 5×ULN and \geq 3×ULN.

ALT values over time will be presented in a spaghetti plot for participants with on-treatment ALT grade 2 or higher elevation (i.e. grade \geq 2) during the OLE period, by treatment group. There will be 1 panel by treatment group. All plots by parameter will have the same scales to allow comparison between groups.

Kaplan-Meier estimates of proportion surviving event-free as a function of time will be presented for the following 4 types of events based on the ALT and eGFR parameters:

- Time from OLE first dose to first occurrence of ≥ grade 2 ALT (days) (for participants with OLE baseline grade < 2)
- Time from OLE first dose to first increase in ALT ≥ 1 grade above OLE baseline grade (days)

- Time from first Evobrutinib dose to first increase in ALT ≥ 2 grade above baseline grade (days) in DBP+OLE
- Time from first Evobrutinib dose to first increase in ALT ≥ 3 grade above baseline grade (days) in DBP+OLE.
- Time from OLE first dose to first occurrence of eGFR assessment equal to less than (<) 60 mL/min for participants with OLE baseline eGFR ≥ 60 mL/min by treatment group (days)

For the above figures based on OLE: time-to-event figures will be based on data from OLE weeks 0-end of treatment; a participant reaching end of treatment, without experiencing the event will have his/her event time right-censored at the time of the last ALT/eGFR assessment. A separate KM curve will be estimated for each of the 5 initial groups: Placebo + Evobrutinib 25 mg QD, Evobrutinib (any dose) and Tecfidera. For the figures based on DBP+OLE: the start time will be the first Evobrutinib dose irrespective of its occurrence during DBP or OLE phase.

To be included in a time-to-event figure, a group must have at least one event. Below the horizontal axis of the time-to-event figure, number of events and number of participants at risk will be displayed every 56 days (OLE period). The vertical axis may be restricted to 0.50 - 1.0, if none of the curves reach 50%.

eDISH (Evaluation of Drug-Induced Serious Hepatotoxicity) figures, as described in Merz *et al* (2014), will be presented for the OLE period. The figure produced will include 6 panels: 1 for each initial dose group and 1 pooled for all the participants who received Evobrutinib during DBP.

Listings containing Lab Test, Analysis Visit, Visit, Date of Measurement (Days under Treatment/ Days under OLE), Time Measurement, Result, Change from Baseline/OLE Baseline, Reference Range Low – High and NCI-CTCAE Grade for ALT, AST, Total Bilirubin and ALP for participants with a post-baseline LFT elevation will be provided for the OLE period.

Listings of Clinical Laboratory Data

By-participant listings of all individual hematology, biochemistry and urinalysis values present in the database will be provided. Only data during the OLE period (including OLE Baseline) will be displayed. A flag will indicate the first visit of switch from Evobrutinib 75 mg QD to Evobrutinib 75 mg BID during OLE period.

Laboratory values that are outside the normal range will be flagged in the data listings, along with corresponding normal ranges.

In this study, clinically significant lab abnormalities were recorded as adverse events. In lieu of a listing of clinically significant lab abnormalities for each domain, the following by-participant lab value listings will be provided:

- Listing of Grade ≥ 3 hematology values with data from DBP and OLE period
- Listing of Grade ≥ 3 biochemistry values with data from DBP and OLE period

• Listing of urinalysis values with Grade ≥ 3, value ≥ 2 times ULN (excluding values for Specific Gravity or pH parameters), or an increase of "++" for non-gradable parameters when applicable with data from DBP and OLE period

Additional analysis on the pancreatic and liver enzymes elevations will be performed.

The following outputs will be provided:

- 1. Kaplan-Meier figure for time to first occurrence of Lipase increased > 2 x ULN and Amylase increased > 2 x ULN separately for DBP and OLE.
- 2. Abnormalities in lipase and amylase (i.e. higher the ULN). For the DBP information to be displayed by original treatment groups. For the OLE period only "Total" is needed.
- 3. Summary of potential DILI by R-Values and Periods for subjects with any ALT or AST elevation for DBP+OLE.

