6.4.4.1 For M2951 Only

The IMP should be temporarily withheld or permanently withdrawn if the following abnormalities occur or reoccur (also see Table 7), as relevant, and reinitiation following temporarily withholding of IMP should be discussed with the Medical Monitor. If a participant's OLE predose or OLE baseline value is abnormal and/or falls within any of the below criteria, consult with the Medical Monitor regarding potential withdrawal, continued participation in study, and additional monitoring if needed. Retesting should be completed within 1 week:

- For a neutrophil count < 500/mm³ or platelet count < 25,000/mm³ (Grade 4) or neutrophil count 500 to 999/mm³ with fever (Grade 3) or platelet count 25,000 to 49,999/mm³ (Grade 3) with bleeding, the IMP should be permanently withdrawn.
- For a Grade 3 decrease in neutrophil count without fever or Grade 3 decrease in platelet count without bleeding, temporarily hold the IMP and recheck the value. If the value is still Grade 3, permanently discontinue the IMP.
- For a Grade 2 decrease in neutrophil count (1,000 to 1,499/mm³) or Grade 2 decrease in platelets counts (50,000 to 74,999/mm³), temporarily hold the IMP and recheck the value. Reinitiate the IMP after discussion with the Medical Monitor if no further downward trend is observed.

The Investigator is required to discontinue the study treatment for abnormal liver function when a participant meets one of the conditions outlined below or if the Investigator believes that it is in best interest of the participant. Liver function test-related monitoring and discontinuation criteria should be based on both central and local laboratory assessments depending on availability (i.e., participants should be discontinued if central or local laboratory result fulfills related criterion). The final decision should be based on the highest reported values (regardless of central or the local laboratory evaluation).

- For an increase in AST and/or ALT to > 3× ULN in combination with an increase in total bilirubin to > 2 × ULN, the study treatment should be permanently discontinued and the Medical Monitor informed. In addition, a comprehensive hepatic/autoimmune panel is required.

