6.12 Medical Care of Participants after End of Trial

After a participant has completed the trial or has withdrawn early, the participant is free to access further treatment as deemed appropriate by the Treating Investigator. The Sponsor will not provide any additional care to participants after they leave the trial because such care should not differ from what is normally expected for participants with relapsing-remitting MS or SPMS with superimposed relapses.

7 Trial Procedures and Assessments

During the Screening Visit, prior to performing any trial assessments that are not part of routine medical care for the participant, the Investigator will obtain written informed consent as described in Section 9.2.

CCI

The maximum amount of blood to be obtained during the trial is within the commonly accepted maximum of 275 mL over 4 weeks and 550 mL over 8 weeks. Details of the blood volumes to be collected for each sample/visit will be detailed in the Laboratory Manual and an estimate is provided in Appendix II. Instructions on how samples will be collected, labeled, processed, stored, and shipped as well as specification on bioanalytical methods will be detailed in the Laboratory Manual.

All blood and urine tests will be analyzed by a central laboratory, with the following exceptions:

- Urine testing for β-human chorionic gonadotropin will be conducted at the local laboratories.
- Urine dipstick results will be interpreted locally. Please see Table 1 for information regarding abnormal dipstick results.

CCI

- HIV testing, when required by local regulation, should be conducted and analyzed locally.
- In addition, ECGs results will be interpreted locally.
- Additional safety monitoring as noted in Section 7.1.3.

The Treating Investigator will be the physician responsible for participant care and should be a neurologist experienced in the care of MS patients. The Treating Investigator will have access to safety and blinded efficacy data and will make treatment decisions based on the participant's clinical response and laboratory findings. The Treating Investigator will also be responsible for the treatment of relapses and determining if nonMS-related factors could account for neurological worsening. The Treating Investigator will determine if a relapse has occurred.

The Assessing Neurologist will be a neurologist or other health care practitioner and must be trained and certified in administering the Neurostatus Functional System Scores and EDSS

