7.1.3 Supplemental Safety Visits

Additional chemistry monitoring (including ALT, AST, alkaline phosphatase, γ -glutamyl-transferase, and bilirubin) will be conducted every 2 weeks until 16 weeks of treatment with evobrutinib (or an increase in the dose of evobrutinib). Subsequently, this will be conducted monthly (every 4 weeks). In the OLE, participants crossing over from the Tecfidera arm to M2951 will have additional safety monitoring conducted as described below.

- In the main study, for all participants in the placebo/M2951 arm, safety visits will be conducted every 2 weeks until Week 40, then monthly at Weeks 44 and 48 (see Table 1).
- During the first 2 years of the OLE period, safety visits will be conducted every 2 weeks until Week 16, then monthly at Weeks 20, 24, 28, 32, 36, 40, 44, 48, 52, 56, 60, 64, 68, 72, 76, 80, 84, 88, 92, and 96 (see Table 2). Subsequently, participants will attend the study site or have a Telephone Visit at least every 6 weeks (see Table 3).
- During the OLE period, additional safety visits will be conducted for participants crossing over from the Tecfidera arm at Weeks 1, 3, 5, 7, 9, 11, 13, and 15.

Safety visits will be conducted after obtaining participant's informed consent. These safety evaluations have been implemented by a letter to Investigators as an urgent safety measure. Given the current status of most participants, these evaluations will start after Week 1 of OLE. It is preferable for chemistry monitoring to be performed at the Investigator's site.

An

additional physical examination may be performed at the Investigator's discretion based on the participant's history at the time of the visit. Any new or change in AEs and concomitant medications should be documented. Patient compliance to additional safety monitoring will be overseen to evaluate continuation in the trial.

These visits should be done at the Investigator's site and blood samples sent to Central Laboratory. In the event that the participant cannot return to the site for the additional blood draws, chemistry monitoring should be done locally; any participants completing a supplemental safety visit locally will not have **CC** collected at that visit.

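### SAP 17.3 takes CTCAE grades from the central laboratory and has no rule for local liver results, while protocol 6.4.4.1 acts on the higher of central and local values

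*SAP*

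**What the plan says.** **Protocol.** Section 6.4.4.1 bases liver monitoring and discontinuation on both laboratories: "participants should be discontinued if central or local laboratory result fulfills related criterion". It then settles any difference between them: "The final decision should be based on the highest reported values (regardless of central or the local laboratory evaluation"). Section 7 sets the default, "All blood and urine tests will be analyzed by a central laboratory, with the following exceptions", and one of the listed exceptions is "Additional safety monitoring as noted in Section 7.1.3". Section 7.1.3 makes central analysis the normal route for those visits too, but adds: "In the event that the participant cannot return to the site for the additional blood draws, chemistry monitoring should be done locally".

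**SAP.** Section 17.3 states: "Gradable laboratory results will be classified according to the grades defined in NCI-CTCAE Version 4.03 as provided by the central laboratory". For AST, ALT and total bilirubin it also says: "The ratios of test result over upper limit of normal (ULN) will be calculated and classified for these 3 parameters during the OLE period". No laboratory source is given for those ratios. The visible SAP text has no rule for grading a local result, for which ULN applies to it, or for choosing between a central and a local value.

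**The concern.** Treatment decisions and the analysis use different definitions of the same liver event. A participant can cross a protocol threshold on a local sample, have drug interrupted or stopped, and have no central sample that shows the peak. If grades come from the central laboratory, that local result has no grade, and every output that needs a grade passes over it.

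Drug-induced liver injury is the important identified risk in protocol 3.2. The sponsor also relies on these displays: SAP version 2.0 was issued partly to add an ALT Kaplan-Meier plot (SAP 4). Any loss here would make the hepatic profile look better than it was.

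**Working it through.** The plan gives no figure on this point to reproduce. The check is a comparison of texts, followed by a simple scaling.

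**1. Outputs that need a grade (SAP 17.3).**
- Shift tables of baseline grade against worst post-baseline grade.
- The ALT spaghetti plot, whose participants are selected by grade 2 or higher.
- Four ALT Kaplan-Meier analyses: two from the first OLE dose and two from the first evobrutinib dose over DBP+OLE.
- The listings of Grade 3 or higher values.

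**2. Liver outputs that do not need a grade (SAP 17.3).** These are the low/normal/high shift tables, the AST, ALT and bilirubin multiples of ULN, the concurrent-elevation categories, eDISH and the R-value summary. The sentence on central grades does not govern them. Their laboratory source is not stated.

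**3. Following a local-only elevation through the plan.**
- *Permanent stop.* Protocol 7.4.1.1 requires a laboratory abnormality that leads to treatment discontinuation to be reported as an AE. It therefore enters the TEAE tables and the tables of TEAEs leading to withdrawal (SAP 17.1.1.1). It also enters the liver AESI if its term is on the list (SAP 17.2.3). It does not enter the outputs in step 1.
- *Temporary interruption.* Protocol 6.4.4.1 calls for this at ALT or AST above 3 and below 5 times ULN. Under 7.4.1.1 it becomes an AE only if there are clinical signs and symptoms or the investigator considers it medically important. It may therefore be missing from both the AE tables and the grade-based outputs.

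**4. The OLE Kaplan-Meier curves.** SAP 17.3 limits these to data from OLE Week 0 to end of treatment and censors non-events at the last ALT assessment. A participant stopped for a local-only elevation is censored at or near the stop, for a reason tied to the event itself, so the censoring is informative. A central sample taken after treatment ended falls outside the curve's data and cannot restore the event. The grade shift tables are more forgiving, because worst values run through Safety Follow-up.

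**5. Direction.** With baseline taken as given, leaving out post-baseline values can lower a worst grade or remove a first occurrence. It cannot raise the one or create the other.

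**6. Size of one missed participant.**
- Total column: about 200 participants are expected in the OLE (protocol 5.1), so 1/200 = 0.5 percentage points.
- One initial treatment group: group sizes in the OLE are not given. Assuming an even split, 200/5 = 40 and 1/40 = 2.5 points. For 30 to 50 per group, 1/30 = 3.3 and 1/50 = 2.0 points.

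**The case against.** The strongest reply is that the two rules serve different purposes. Section 6.4.4.1 is a precautionary rule for the individual. SAP 17.3 sets one uniform grading source for group summaries, and consistent central grading is defensible. Local testing is a fallback. The protocol also asks for follow-up testing and a hepatic panel that includes ALT, AST and bilirubin, so a central sample may well show the elevation. An event is missed only if no central sample within the output's data reaches the grade. All of this stands, and it limits how often the problem can arise. It does not supply the missing rule.

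Three stronger readings are tempting, and the documents do not support them.
- *Local values are excluded from the analysis.* The SAP sentence says where grades come from and does not say "only". SAP 8 uses eCRF and laboratory data without restricting the source, and 17.3 lists all individual values in the database.
- *Elevations that stop treatment disappear from the report.* They do not, because of the AE route in step 3 of the working. But an AE record does not place an event in a grade shift table or a Kaplan-Meier curve, and it does not reliably cover temporary interruptions.
- *The reported rate of ALT at or above 3 times ULN is understated by some percentage.* That table is built on ratios and is not governed by the grading sentence. The documents give no share of elevations seen only locally, so any such percentage would be invented.

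**Conclusion.** The mismatch is real and confined to the grade-based laboratory outputs. Followed as written, the SAP leaves a local-only ALT, AST or bilirubin elevation ungraded although the protocol acts on it, and the OLE ALT curves then censor that participant informatively. For the ratio-based outputs, eDISH and the R-value summary, the defect is an unstated source and not a contradiction.

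The total effect cannot be calculated, because the number of local-only elevations is not given. Per participant it is about 0.5 points in the total column, and 2.0 to 3.3 points in a treatment group under the assumed 30 to 50 per group. This rests on reading the central-grade sentence literally and on at least some local results existing. The error can only favour the drug on an identified risk, so a stated rule is worth having even if few participants are affected.

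**What to change.** In SAP 17.3:
- State that local ALT, AST, ALP and total bilirubin results held in the database are divided by their own laboratory's ULN and graded by program with CTCAE 4.03.
- Produce the grade-based liver outputs on the highest available value. For consistency, do the same for the multiples-of-ULN table and eDISH. This can be the main analysis or a sensitivity analysis, shown beside the central-only version.
- State the laboratory source of the R-value summary.
- Flag local values in the listings.
- If local values or their ULNs were not collected, say so as a limitation, because a change of wording cannot recover them.

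The cost is SAP text and some programming. Taking the highest value mixes assays and gives participants who are tested more often more chances to reach a threshold. The own-ULN ratio limits the first problem, and the central-only version shows how much either one matters. No clinical stopping rule changes.
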